1.6 Rationale and hypotheses for the current study

The conclusion of reviews of research supports the need for further research in the form of randomised controlled trials, as do the recommendations from the studies cited above. The proposed study will be larger than previous studies and include assessment of change on the primary outcome measure of COPD specific health status (the COPD Assessment Test, CAT), immediately after a three-month programme of regular singing, and on further three month follow up. The primary research null hypothesis will be that: 'No change occurs in COPD-specific health status, following ten weeks of regular, weekly singing at the primary end point for the trial six months post-baseline.'

A particular challenge is establishing real-time records of patterns of respiratory function to test a secondary hypothesis that regular singing leads to change towards deeper breathing supported by the diaphragm. One technique which may do this is structured light plethysmography (SLP) where movements of the chest wall and abdomen can be recorded for individuals as participants' breath. A small, feasibility exercise assessing the value of this technique for the current study has been undertaken (see above). The supplementary null hypothesis will be that: 'No changes occur in key parameters (specified below) derived from structured light plethysmography reflecting movement of the chest and abdomen during breathing, following three months of regular singing, at the primary end point of the trial six months post-baseline.'

Further secondary hypotheses will be tested for potential changes three months post-baseline at the conclusion of the singing programme.

Singing and COPD protocol version 1, 18 December, 2018

As, following randomisation, participants will inevitably be fully aware of their allocation to singing group or control, the trial cannot be double-blinded. However, in follow-up assessments, the staff conducting the measurement procedures will be blind to trial allocation.

1.7 Public and patient involvement

Considerable care has been taken in the design of the current study to consult with patients affected by COPD and interested members of the public (including family members of people with COPD), drawing on participants of singing for better breathing groups previously established by the De Haan Centre and which have continued to meet. A member of the research team has a diagnosis of COPD. In addition, people with COPD and other members of the lay public were formally invited to review the protocol in the course of its development. The Trial Management Committee will also include patients affected by COPD and lay members.

Table 1. Research with controls

Reference	Number of participants (intervention vs control)	Intervention	Control	Measures	Findings	Conclusions
Bonilha et al 2009	Randomised 15:15	1 hr weekly singing for 24 weeks. Relaxation, respiratory & vocal exercises then Brazilian folks songs. Enc home practice	Handcraft work 1 hour weekly over 24 weeks. Relaxation exercises. Including home practice	Pulmonary function, SGRQ, QoL and Borg scale	Intervention group showed small improvement in maximal expiratory pressure, control group declined. Both groups increased their scores on SGRQ	Regular singing may improve QoL and improve maximal expiratory pressure. Additional studies recommended to define role of singing as potential to assist PR
Lord et al 2010	Randomised 15:13	1 hr sessions for 6 weeks of twice weekly singing.	Usual care	SF36, HADS, single breath counting, breath hold, walk test	Significant improvements in anxiety (HADS) and physical component of SF36 in intervention group	Singing classes can improve QoL and anxiety but did not improve measures of breath control or functional capacity. Further work needed to quantify magnitude and duration of improvement
Lord et al 2012	Randomised 13:11	1 hr sessions twice weekly for 8 weeks. Includes vocal exercises, posture and relaxation training. Homework CD.	Weekly Film club for 8 weeks followed by group discussion	HADS, CAT, SF36, walk test, Borg scale, single breath holding	Significant improvements in the physical component of SF36 in intervention group.	Participation in singing lessons may be a useful activity for people with COPD
Goodridge et al 2013	Consecutive assignment 14:5	1 hr weekly sessions post PR for 8 weeks led by music therapist. Plus relaxation, resp. & vocal exercises. Request to practice at home.	Usual care (PR)	SGRQ, walk test, Illness perception questionnaire	No significant changes on SGRQ or walk test.	Ongoing work is needed to establish whether longer duration and intensity of singing demonstrates improvement

Table 2. Quantitative studies without controls

Reference	Number completing	Design	Intervention	Measures	Findings	Conclusions
Engen 2005	7	Cohort pre-test-post-test	45 min sessions twice a week for 6 weeks. Inc warm-up exercises	Physical health, functional outcomes and QoL	No sig difference in physical or functional outcomes. Breath control and voice intensity showed sig improvement. QoL results mixed. Breathing mode changed to diaphragmatic.	Vocal instruction + breathing exercises may help improve QoL of senior citizens with emphysema. Further investigation of the treatment method is warranted.
Morrison et al 2013	72	Cohort pre-test-post-test plus midpoint testing	6 singing groups set up. 90 min sessions over 36 weeks. Inc relaxation, posture, breathing and vocal exercises.	SCRQ, MRC scale, EQ-5D, York SF-12 at baseline, midpoint and end. Pulmonary function at base and end	QoL (SGRQ) showed sig. improvement. Improvement in spirometry measures.	Community singing can have an exercise training effect on lung function of people with mild to very severe COPD. Need for a larger-scale controlled study.
Waugh et al 2015 (unpublished)	8	Cohort pre-test-post-test	1.5hr singing twice a month plus breathing exercises	AQ20 (QoL measure)	5 of 8 improved score but no significant differences	Singing is a low-cost, enjoyable way to improve health of pts with respiratory conditions
McNaughton et al 2017	21	Feasibility cohort pre-test-post-test plus midpoint testing	1 hr a week for a year, including warm-up and cooling down. Home practice encouraged with recording.	Pulmonary function, Clinical COPD questionnaire, HADS and walk test	Significant reduction on HADS anxiety score at 1 yr. Walk distance increased at 4 mo. & 1 yr. No improvement or deterioration in pulmonary measures.	Findings support feasibility of long-term participation in a community singing group for adults with COPD who have completed PR. Results can inform sample size and choice of measures for RCT
Clift et al 2017	44 (questionnaire) 42 (lung assessment)	Feasibility, 2 cohort pre-test-post-test	4 groups set up. 90 min weekly sessions over 38-40 weeks. Included relaxation, posture, breathing and vocal exercises	SGRQ, MRC scale, EQ-5D, pulmonary function, walk test, Borg scale.	No sig. improvement in respiratory function (except for one measure, which may be incidental). Sig reduction in SGRQ symptom scale	As a feasibility study, project ran successfully. Larger trials need to establish impact of singing for lung health.
Lewis et al 2018	113 (47% had COPD) from 26 BLF groups	Baseline & 3 months.	60-90 min weekly singing + breathing, posture & vocal ex.	CAT, EQ-5D-3L (VAS only), MRC scale, GAD-7, Patient activation score	Sig improvement in CAT score and GAD-7 anxiety	Endpoints should be evaluated with large-scale RCTs.

Table 3 Qualitative studies

Reference	Data collection	Number of participants	Summary findings across studies
Lord et al 2010	Interviews	8	
 □ Physical: Control of breathing, understanding and managing condition day to day, posture improvement, increase in energy. □ Mental: Mental wellbeing, improved mood, including pleasure, distraction, safe space, sense of achievement and purpose, confidence, generalise into life outside group. □ Social: Support, part of a community, connections
Lord et al 2012	Interviews	5	
Skingley et al 2014 (included in Morrison et al 2013)	Written comments	97	
McNaughton et al 2016 (included in McNaughton et al 2017)	Interviews, focus group	12 and 11	
Skingley et al 2018 (included in Clift et al 2017)	Interviews	37	

Table 4 Reviews

Reference	COPD studies included	Conclusions	Recommendations
Gick & Nicol 2016	Bonilha et al 2009; Engen 2015; Goodridge et al 2013; Lord et al 2010, 2012; Morrison et al 2013.	Limited or inconsistent improvements in COPD symptoms or objective breathing measures. Benefits may be due to enjoyment.	Need for longer term outcomes. Emphasise possible psych and social benefits to increase recruitment and collect data on beliefs about value of singing.
Lewis et al 2016	Bonilha et al 2009; Lord et al 2010, 2012; Morrison et al 2013.	Singing for lung health may improve physical health status and quality of life in COPD.	Larger and longer studies are needed with economic outcomes.
McNamara et al 2018	Bonilha et al 2009; Lord et al 2010, 2012.	Low to very low evidence that singing improves physical health on SF-36. Small samples. Few studies of singing in conjunction with PR.	More RCTs and larger samples are needed.
Daykin et al, 2016	Lord et al 2012; Skingley et al, 2014	Low quality evidence points to wellbeing outcomes for people with COPD	There are challenges to establish evidence due to the diversity of research approaches and measures used.

2 Methodology

2.1 Design, questions, aim and objectives

Design

The planned study is a single-blinded randomised controlled trial which will compare participation in a structured singing programme over 10 weekly sessions, with a usual treatment control. A 3 by 2 mixed anova design will be adopted with time as the within subjects factor at 3 levels (baseline, end of intervention and follow-up) and Condition as the between subjects factor with 2 levels (singing vs. control).

Questions

The study seeks to answer the following questions:

1. Is a ten-week progressively structured programme with recommended weekly practice between sessions acceptable, manageable and enjoyable for participants in the trial?
2. Does regular singing help to improve the perceived health and quality of life of patients with COPD over and above the provision of usual treatment?
3. Does regular singing result in a changed pattern of breathing in COPD patients with a shift towards breathing supported by the diaphragm, and a longer, slower controlled out-breath?
4. Does regular singing help patients with COPD manage the demands of daily living more effectively?
5. Does regular singing compared with usual treatment lead to a reduction in the use of medication and health services that will result reduced in care costs?

Aim and objectives

The overall aim is to conduct a pilot single-blinded randomised controlled trial, to evaluate the health benefits of a community singing group for patients with COPD in Medway, Kent. We are interested in finding out whether participating in community singing helps to improve the quality of life of patients with COPD.

Principal objectives are formulated around the primary outcome measure for the study, and a number of secondary outcomes. Service use will be assessed. There will also be an embedded qualitative study of patients' experiences of the singing programme, and the extent to which they follow guidance on practising breathing exercises and singing between group sessions.

Primary Outcome

- Impact on quality of life and management of breathing difficulties (as assessed by CAT) (Jones, et al., 2009; Kon, et al., 2014; Jones, et al., 2014; CAT, 2016)

Secondary Outcomes

- nMRC breathlessness scale (see: <https://mrc.ukri.org/research/facilities-and-resources-for-researchers/mrc-scales/mrc-dyspnoea-scale-mrc-breathlessness-scale/%EF%BB%BF> Williams, 2017; Fletcher et al., 1959)
- SF-36 v2, Physical health related quality of life and Mental health related quality of life (Jenkinson et al., 1999) (Available from Optum: <http://campaign.optum.com/optum-outcomes/what-we-do/health-surveys/sf-36v2-health-survey.html>)
- Generalised anxiety disorder (as assessed by GAD-7) (Spitzer, et al., 2006)
- Depression (as assessed by PHQ-9) (Kroenke, et al., 2001)
- Anxiety (as assessed by GAD-7) (Kroenke, et al., 2002)
- Lung function and patterns of breathing (as assessed by spirometry and SLP – for further details see below)
Functional exercise (as measured by the 6MWT – further details below)
Use of inhalers, consultations with health professionals and hospital admissions

The standardised measures employed in this trial have been chosen based on previous research on singing and COPD, the outcome of recent systematic reviews (Lewis et al., 2016; McNamara et al., 2017, and the latest guidance on the assessment and diagnosis of COPD (NICE, 2018). All questionnaires have been screened and assessed for suitability as ‘patient reported outcome’ measures using the checklist devised by Francis et al. (2016) (see Appendix 7.10).

We are using CAT, GAD-7 and PHQ-9 as these measures are routinely used by the Medway Community Healthcare Respiratory team in the monitoring of responses to pulmonary rehabilitation.

CAT serves as a COPD-specific quality of life measure and is especially suited to being the primary outcome measure for the study. There is also an established ‘minimum clinically importance’ change score of two points (Kon et al., 2014), and this will provide an important criterion against which to judge the outcome of the trial for clinical purposes.

Both GAD-7 and PHQ-9 have established cut-off points for increasing grades of severity on mental health condition, and will serve to assess the extent to which participants in the trial can be regarded as experiencing clinically significant levels of mental health challenge, and whether this changes over the course of the trial for the intervention group relative to the control. It is recognised also that the two mental health scales can be combined to form a single measure of anxiety-depression.

The SF-36 will also be used as this measure was employed in both Brompton studies (Lord et al., 2010, 2012), and revealed significant changes on the physical health related quality of life scale, with a large effect of approximately 1. The current study will employ the current version 2 of the SF-36 as opposed to the earlier version used in the previous Brompton studies. This is justified as V2 is the most recent version and we will have the benefit of technical support from Optum, the owners of the scale, together with access to the most recently available and appropriate norms for scoring. We assume that scores arising from the earlier and current version would be virtually identical.

The MRC breathlessness scale (nMRC, see Williams, 2017) will be employed as a score of 3 (out of a score range of 0-4) is often used as a criterion for recommending pulmonary rehabilitation (PR). As this trial will target recruitment towards patients who have undergone or who are receiving PR, it is expected that all participants will have an nMRC score of 3 or 4.

Details of spirometry, SLP assessments and the 6MWT parameters are given in section 2.6 below

2.2 Participants

In this study, the participant population will come from the population of COPD patients supported by the Respiratory Service of Medway Community Healthcare. Participants will be recruited from patients who have received PR and those who are currently undergoing PR. The study will seek to achieve a final sample of 80 patients at the second follow-up – 40 in the intervention arm and 40 in the control arm. The intention is to recruit 100 patients who consent to allow for 20% attrition. It is expected that we will need to secure initial expressions of interest from at least 120 people to allow for drop out even prior to consenting.

The number of participants is based on the resources available to run the trial, and no formal power calculation has been used to determine the sample size to be recruited. There is an important ethical issue raised by running a trial that is potentially under-powered. As Freedman et al. (2001:401) put it:

Sample size and power must be addressed before the start of a randomised, controlled trial. It is necessary to know in advance the likelihood of finding valid conclusions from the population assessed. It may be acceptable to subject a patient to a chance of a less than ideal treatment, or to the psychological stress of being a 'subject', if there is a chance of a valid scientific outcome, but it is not ethical to conduct a study the design of which cannot make valid conclusions.

However, relevant considerations are:

- There is no reason to think that participation in the trial will pose any risks to the participants, nor subject them to 'less than ideal treatment' or undue psychological stress. All of our experience with running previous studies in East Kent and Lambeth and Southwark, and the feasibility study in Medway is that participants will find the singing intervention enjoyable and personally and socially beneficial.
-
- The Brompton trials (Lord, 2010, 2012), involved 28 and 24 participants respectively, and reported significant changes in the physical component of the SF-36. The proposed study will be three times larger.
-
- The Medway feasibility study (see above) showed an improvement on the CAT questionnaire of five points, more than twice the minimum clinical difference score of two. A change of five points represents a moderate effect size of approximately 0.5. If such a difference arises between the intervention and control groups in the proposed trial, where data is paired from pre-test and follow up, a sample size of 40 per group will be more than sufficient to give 90% power at a p-value of 5% (two-tailed) (Chan, 2003).
-
- The proposed study will assess participants immediately following the intervention and then after a further three months. No such follow-up has taken place in previous trials.

- The current study is a pilot and if the findings are encouraging the results could be subsumed into a larger multi-centre trial conducted in the same way.

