1.5 Feasibility studies in Medway

Singing for Better Breathing

As a basis for assessing the feasibility of setting up and running a randomised controlled trial in Medway and in association with Medway Community Healthcare Respiratory Team, two 'singing for better breathing' groups were established in Medway in May, 2017. Participants were recruited through visits to pulmonary rehabilitation classes (PR) run by the respiratory team in two community venues. Members of the De Haan Centre spoke about the idea of 'singing for better breathing' and ran taster exercises. Interest levels were high with approximately half of PR participants expressing a willingness to participate in singing groups. Two groups were set up in Gillingham and St. Mary's Island, and of the people expressing interests at PR, approximately half were able to join one of the groups (i.e. 25% of those contacted initially). This suggests that in recruitment for a further study, at least four times the required sample would need to be reached through direct contact.

The two groups ran weekly over three months, and participants were guided through a structured progressive programme of exercises and singing in line with the approach adopted in previous

studies conducted by the De Haan Centre. In addition, participants were given a printed resource and access to video of exercises and singing to support individual practice at home between sessions.

The singing programme was evaluated by [name] as part of her PhD research within the De Haan Centre, and three measures were employed in a simple baseline-follow up design: the COPD Assessment Test (CAT), the Asthma Control Questionnaire (ACQ) and the Warwick Edinburgh Mental Wellbeing Scale (WEMWBS). The table below gives the means on these questionnaires at baseline and after the programme, and show clearly that significant improvements took place on the CAT and WEMWBS with a marginally significant improvement on the Asthma Control Questionnaire.

Scale	Sample	Baseline	Follow-up	t	p
CAT	21	25	20	2.75	0.01
WEMWBS	21	49	55	-2.61	<0.02
ACQ	20	12	10	2.01	<0.10

The results from the CAT questionnaire were especially encouraging, as the improvement of five points on the scale is clearly greater than the established 'minimal clinically important' change score of two points (Kon et al., 2014).

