effect/analyses	expected difference	Notes	required N for minimum .80 power and alpha at .05 with moderate effect size d=.5		
anova - main effect of time	not relevant		34		
anova - main effect of condition	not relevant		86		
anova - interaction	significant		36		
anova - main effect of condition within T1	non significant		146	Bonferroni corrections included	sensitivity power analyses revealed that the minimum effect size detectable with power of .80 and sample size of 40 in each group is d=.68
anova- main effect of condition within T2	significant	the effect sizes of these two effects can be compared to test for prolonged effects of the intervention	146	Bonferroni corrections included	
anova - main effect of condition within T3	significant (but smaller than above)		146	Bonferroni corrections included	
anova - main effect of Time within Intervention Condition	significant		28		
anova - main effect of Time within TaU Condition	non significant		28		
anova - post hoc on main effect of Time within Intervantion Condition	significant between T1 and T2 but possibly disappearing between T2 and T3		39	Bonferroni corrections included	
anova - post hoc on main effect of Time within TaU Condition	not relevant		39	Bonferroni corrections included	

7.15 – Medway Singing and COPD Programme

The design of the singing programme is based on facilitator experience and participant feedback from singing for health projects conducted by the Sidney De Haan Research Centre over the past ten years. Each session will commence with physical and vocal warm-ups to prepare and protect the voice. These range in intensity and demand and are designed to provide a common focus, as well as encourage participants to learn to gain control of their breathing prior to singing.

Participants will be guided through a variety of songs, which gradually demand greater breath control and vocal production during the course of the singing sessions. Repertoire will include songs with short and long phrases, and a blended approach in each session will encourage confidence and breath-control. In addition, material will be utilised which encourages strong diction and vocal projection, both of which require consideration of breath control and management. Potential limitation in vocal range will be carefully addressed, with consideration given to the key and notation range in each song.

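### The statement that 40 per group more than suffices for 90% power is wrong on the protocol's own figures, which give about 60% unadjusted and about 83% baseline-adjusted at an implied correlation of .65

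*Protocol*

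**What the plan says.** Section 2.2 states that resources fixed the sample size and that "no formal power calculation has been used to determine the sample size to be recruited". It aims for 80 patients with final follow-up, "40 in the intervention arm and 40 in the control arm", and concedes that the trial may be under-powered. It then lists considerations in the trial's favour. One of them starts from the Medway feasibility study: "A change of five points represents a moderate effect size of approximately 0.5". It continues: "If such a difference arises between the intervention and control groups in the proposed trial", "where data is paired from pre-test and follow up", then "a sample size of 40 per group will be more than sufficient to give 90% power at a p-value of 5% (two-tailed").

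The feasibility result is in the table in section 1.5 (scale, sample, baseline, follow-up, t, p): "CAT 21 25 20 2.75 0.01".

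The statistical analysis plan table in Appendix 7.14 gives required N for 80% power at d = .5. For the effect of condition at T2 or at T3 it asks for 146, Bonferroni correction included. Its sensitivity note says that the "minimum effect size detectable with power of .80 and sample size of 40 in each group is d=.68". For the interaction it asks for 36. It expects the condition effect at T3 to be smaller than at T2. Section 1.6 places the primary endpoint six months after baseline.

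**The concern.** The sentence gives a power for a difference between two independent arms but appeals to pairing within person. Pairing baseline with follow-up can reduce the error variance. It does not turn singing versus control into a paired comparison, and the gain depends on a correlation that the protocol never states. The result also looks incompatible with the appendix: 40 per group cannot give over 90% power at d = 0.5 and yet need d = .68 for 80% power in a comparison of the same arms, unless the two statements concern quite different tests.

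Section 2.2 itself raises the ethics of running an under-powered trial, and among the considerations it offers in reply this is the only one that states a power. A reader who relies on it would expect a non-significant result to be informative about a 5-point difference, and perhaps about the 2-point minimum clinically important difference that section 2.1 makes a criterion for judging the trial.

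**Working it through.** **Inputs**
- n = 40 per arm, two-sided 5% (section 2.2).
- Difference 5 CAT points, d about 0.5 (section 2.2). This implies SD = 5/0.5 = 10, which is not stated.
- Feasibility study: n = 21, mean 25 to 20, t = 2.75 (section 1.5).

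**Formula.** Between arms, power comes from the noncentral t with 2n − 2 = 78 degrees of freedom and noncentrality d × √(n/2) = d × 4.47.

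**1. Trying to reproduce 90%**
- One-arm paired test at d = 0.5: 40 gives 86.9%, and 44 are needed for 90%.
- One-arm paired test at the feasibility value, dz = 2.75/√21 = 0.60: 40 gives 96%, and 32 are needed for 90%.

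Neither is a comparison between arms, and the first falls short of 90%.

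**2. Power for the between-arm difference described**

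| Analysis | Derivation | Standardised difference | Power at 40 per arm | n per arm for 90% |
|---|---|---|---|---|
| Unadjusted | 5/10 | 0.50 | 59.8% | 86 |
| Change score | SD of change = 5 × √21/2.75 = 8.33; 5/8.33 | 0.60 | 75.5% | 60 |
| Baseline-adjusted (ANCOVA) | r = 1 − 8.33²/(2 × 10²) = .653; SD = 10 × √(1 − .653²) = 7.57; 5/7.57 | 0.66 | 83.0% | 50 |

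The r in the last row assumes equal SDs at both times. Reading approximately 0.5 as 0.45 to 0.55 moves the ANCOVA power only from 81.6% to 84.7%.

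**3. Dependence on r (ANCOVA, SD 10, 40 per arm)**

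| r | .3 | .5 | .6 | .65 | .7 | .73 | .75 | .8 |
|---|---|---|---|---|---|---|---|---|
| Power | 64% | 72% | 79% | 83% | 87% | 90% | 92% | 96% |

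Treated as an ordinary correlation from 21 people, r = .65 has a rough 95% interval (Fisher z, 0.78 ± 1.96/√18) of .31 to .85. The implied value is therefore weakly determined.

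**4. The appendix**
- The 146 is a total. Scaling the sensitivity figure gives 40 × (.68/.50)² = 74 per arm, against 146/2 = 73.
- One-sided .05/3 comes close to both figures (total 144, smallest detectable d .674). Two-sided .05/3 does not fit (172 and .74).
- So for the condition effect at T3 with d = .5, the appendix wants 73 per arm for 80% power, where section 2.2 says 40 is more than enough for 90%.

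**5. Precision at 40 per arm, SD 10**
- Smallest difference detectable with 80% power, unadjusted: 0.634 × 10 = 6.3 points.
- 95% CI half-width, unadjusted: 1.99 × 10 × √(2/40) = 4.45 points.
- Adjusted at r = .65: 4.45 × .757 = 3.37 points.

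**The case against.** **The sentence is conditional and sits among candid disclosures.** The protocol calls the trial a pilot, says that resources set its size, and publishes the d = .68. The sentence set neither the sample size nor the analysis. This limits the harm, and a misreading of a null result is a risk rather than a certainty. It does not make the stated power right.

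**The appendix is not uniformly at odds with the text.** The planned analysis is a 3 by 2 mixed ANOVA, and the interaction row needs only N = 36. Taken alone, that row does not conflict with section 2.2. The 146 carries a Bonferroni correction and concerns one time point, so the two places partly describe different tests. This stands, and the conflict should be confined to the T2 and T3 condition rows and the sensitivity note. The interaction row gives limited comfort, however. A 0.5 SD difference present only at T2 and T3 is an interaction of f about .118, smaller than the f = .25 that corresponds to d = .5. Power at N = 80 is then about 62% at r = .5 and 79% at r = .65.

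**A reader might infer that 83% is a ceiling, or that no calculation gives 90%.** The documents do not support either. The 83% rests on a back-calculated r; ANCOVA reaches 90% from r of about .73, and the within-arm test at dz = 0.60 gives 96%.

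**A reader might also infer that a paired formula was misapplied.** The mention of pairing, and the 44 pairs needed at d = 0.5, make this plausible. The calculation rests on a cited source that is not to hand, so it remains inference.

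**Conclusion.** The sentence is wrong as written. For a 5-point difference between arms with 40 in each, the protocol's figures give about 60% power unadjusted, about 76% on change scores and about 83% baseline-adjusted at r of about .65. Reaching 90% needs r of about .73 or more, which the protocol neither states nor implies. These results assume SD 10, from the stated equivalence of 5 points with about 0.5 SD, and take the SD of change from 21 people. The ANCOVA figure also assumes an analysis that the protocol does not name.

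The sentence conflicts with Appendix 7.14 on the condition effect at T2 and T3 and on the d = .68, though not on the interaction row. The assumed effect is also optimistic for its purpose: it is a before-after change without controls, measured at the end of a programme, while the primary endpoint falls at six months, where the appendix expects a smaller effect. How much smaller is not stated.

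With a half-width of about 3.4 to 4.5 points, a non-significant result would not by itself exclude a 2-point benefit.

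**What to change.** Delete the 90% sentence from section 2.2 and replace it with text along these lines:

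> With 40 completers per arm, two-sided 5% and an assumed CAT SD of 10, power for a 5-point difference between arms at six months is about 60% unadjusted. If a baseline-adjusted comparison is used, it is about 72% to 90% for an assumed baseline to follow-up correlation of .5 to .73. The smallest difference detectable with 80% power is about 6.3 points unadjusted. The expected 95% CI half-width is about 4.5 points unadjusted and about 3.4 points adjusted at a correlation of .65, so a non-significant result does not by itself exclude the 2-point minimum important difference. The 5 points come from an uncontrolled before-after change at the end of a programme.

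The adjusted figures belong in the text only if the protocol names a baseline-adjusted comparison as the analysis; at present it names a mixed ANOVA. Reconcile the paragraph with the d = .68 in Appendix 7.14, and say there that 146 is a total and which alpha the Bonferroni correction uses.

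The cost is wording only. The stated power becomes less favourable, and no extra patients are needed.
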